8. OVERALL CLINICAL TRIAL SCHEDULE

The current trial will include 7 planned clinical visits at the investigational site and 1 follow-up telephone call. A detailed flow chart showing the procedures performed is given in [Appendix 1](#). The following sections outline the procedures to be performed at the individual visits.

8.1. VISIT 1 - SCREENING VISIT (WITHIN 30 DAYS OF VISIT 2)

At Visit 1 (Screening), the following procedures will be performed:

- obtain written Informed Consent;
- documentation of medical history and subject demographic data;
- documentation of previous and concomitant medications (including long term antibiotic use for NCFB pulmonary infection prophylaxis, and in particular oral azithromycin/erythromycin/clarithromycin administration in the last 12 months, and any prior use of nebulised colistin or colistimethate sodium or other inhaled/oral antibiotic);
- check number of NCFB pulmonary exacerbations in the preceding year;
- check of inclusion/exclusion criteria;
- assessment of vital signs ([Section 9.1.3](#));
- physical examination (including chest auscultation);
- 12-lead ECG in the supine position after 5 minutes of rest (evaluation by local medical staff) in order to verify the subject's eligibility ([Section 9.1.6](#));
- blood samples for clinical laboratory assessments (haematology, clinical chemistry and renal function tests). ([Section 9.1.4](#));
- dip-stick pregnancy test for women of child-bearing potential.
- spirometry (if not done in the 30 days beforehand); pre-bronchodilator FEV₁ must be ≥30% of predicted for the patient normal value (determined using Global Lung Function Initiative [GLI] reference equations);

- collection of CCI [REDACTED] (results have to be available by Visit 2; if negative, the subject will be asked to return to the clinic for a repeat sputum sample prior to Visit 2 - if this second sample is also negative, one further sample may be collected for analysis; thereafter, the subject will be a screen failure and will not be required to attend Visit 2);
- instruction of subjects on actions to be taken in case of NCFB pulmonary exacerbations.

The Investigator will arrange an appointment for Visit 2 within 30 days.

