7.2. SELECTION OF SUBJECTS

7.2.1. INCLUSION CRITERIA

Subjects can be included in the trial if they meet all the inclusion criteria listed below:

- 1) are able and willing to give informed consent, following a detailed explanation of participation in the protocol and signed consent obtained;
- 2) are aged 18 years or older of either gender;
- 3) are diagnosed with NCFB by computerised tomography (CT) or high resolution CT (HRCT) as recorded in the subject's notes and this is their predominant condition being treated;
- 4) had at least 2 NCFB pulmonary exacerbations requiring oral or inhaled antibiotics or 1 NCFB pulmonary exacerbation requiring intravenous antibiotics in the 12 months preceding the Screening Visit (Visit 1) and had no NCFB pulmonary exacerbation with or without treatment during the period between Visit 1 and Visit 2;
- 5) have a documented history of *P. aeruginosa* infection;
- 6) are clinically stable and have not required a change in pulmonary treatment for at least 30 days before the Screening Visit (Visit 1);
- 7) have pre-bronchodilator FEV₁ \geq 25% of predicted;
- 8) had a positive sputum culture for *P. aeruginosa* from an adequate sample taken at the Screening Visit (Visit 1) or during the screening period.

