9.1.6. SAFETY EVALUATIONS

Adverse Events

AEs will be recorded by the Investigator in the appropriate eCRF Section starting with the date of informed consent until the follow-up phone call. At each contact (i.e. clinical visit or phone call), subjects will be asked in a non-leading manner if they experienced any AEs.

All AEs occurring from the day of the first IMP administration, i.e. Visit 2, until the end of the trial, i.e. follow-up phone call, will be considered as TEAEs.

(Note: A pulmonary exacerbation will be reported as an AE or serious AE [SAE]; pulmonary exacerbations will also be captured as efficacy assessments).

For definitions and reporting of AEs and SAEs, see [Section 16](#).

Lung Function by Means of Spirometry

Spirometry measurements of FEV₁ and FVC (predicted values will be as per GLI reference equations [23]) will be performed at Visit 1 (if not performed in the preceding 30 days) to verify the eligibility of the subject (see inclusion criteria in [Section 7.2.1](#)), and at Visit 2 through Visit 7.

Lung function measurement and daily calibration of the spirometer will be performed according to the standardised methods described by the American Thoracic Society/European Respiratory Society. It is suggested that, in each centre, the model of the spirometer used does not change during the study.

Lung function measurements will be done at approximately the same time of the day during clinic visits (dependent on IMP administration) with subjects either standing or sitting (for each subject, this should be consistent throughout the trial) with the nose clipped after at least 10 minutes rest. Calibration of the spirometer must be performed preferably by the same Investigator at each visit prior to spirometry measurements and the reports must be kept with the source trial documents.

For FEV₁ and FVC the highest value from 3 technically satisfactory attempts will be considered (irrespective of the curve they come from).

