Section 6.2: Duration of Clinical Trial	The anticipated quarter for last subject out has been revised.	The date for last subject out has been amended to Q4 2020 to reflect the increased recruitment period required to achieve the required sample size.
Section 7.2.1: Inclusion Criteria	Inclusion criteria #3 has been amended from “diagnosed with NCFB by computerised tomography (CT) or high-resolution CT (HRCT) as recorded in the subject’s notes” to “are diagnosed with NCFB by computerised tomography (CT) or high-resolution CT (HRCT) as recorded in the subject’s notes and this is their predominant condition being treated”.	Amended to emphasize and clarify that NCFB should be the predominant condition experienced by the study patient requiring treatment (as opposed to, for example, chronic obstructive pulmonary disease.
	Inclusion criteria #4 amended to allow patients experiencing 2 NCFB pulmonary exacerbations requiring inhaled antibiotics to be enrolled.	Discussions with sites have indicated that inhaled antibiotics are routinely being used at several sites and not just oral antibiotics as routine management for patients with NCFB pulmonary exacerbations.
	Inclusion criteria #7 has been amended to allow patients with a pre-bronchodilator FEV ₁ ≥25% (as opposed to ≥30%).	The FEV ₁ level has been adjusted downwards after consultation with experts in the field who agree this cut off level would not negatively impact the study in terms of safety but would help with recruitment.
	Inclusion criteria #8 has been amended to reflect the fact that any positive result for one of the three potential sputum samples collected during the periods between Visit 1 and Visit 2	Amended to reflect the sputum sample collection details documented in relevant sections of the study protocol.

	allows for patient inclusion.	
Section 7.2.2: Exclusion Criteria	Exclusion criteria #3 has been amended to remove the reference to myeloproliferative disease.	This was an exclusion criterion in the Zambon phase 2 trial but has not been an exclusion criteria in similar phase 3 trials. Removal of this exclusion criteria will have no negative impact on the safety of the trial or efficacy assessments. There are no known confounding factors with NCFB and myeloproliferative disease. Other exclusion criteria will ensure patient safety; in particular exclusion criteria #20 (as renumbered).

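### Section 8.1 of the protocol screens at FEV1 of at least 30% predicted while inclusion criterion 7 admits at least 25%, so one measurement carries two eligibility thresholds

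*Protocol*

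**What the plan says.** Inclusion criterion 7 appears twice in the protocol, in the Summary (Section 2) and in Section 7.2.1. Both set the lower limit for pre-bronchodilator FEV1 at "25% of predicted".

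Section 8.1 lists what sites do at Visit 1. Its spirometry item makes it a requirement that pre-bronchodilator FEV1 be at least "30% of predicted for the patient normal value", using the Global Lung Function Initiative equations. The same list includes the item "check of inclusion/exclusion criteria", so criterion 7 is applied at that visit too. Section 9.1.6 states that Visit 1 spirometry is done "to verify the eligibility of the subject (see inclusion criteria in" Section 7.2.1).

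The summary of key changes attached to version 7.0 explains the background: "Inclusion criteria #7 has been amended to allow patients with a pre-bronchodilator" FEV1 of 25% or more, where the limit had been 30%. It gives this change for Section 2 and for Section 7.2.1. Its visible entries then go from Section 7.2.2 to Section 8.2, with none for Section 8.1.

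**The concern.** An eligibility threshold has to be a single number wherever staff will look for it. Here the criteria list and the visit procedure disagree by 5 percentage points of predicted FEV1, and each is worded as mandatory. The protocol plans approximately 100 sites in an estimated 15 countries, so different readings are foreseeable.

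Two things are at stake. The first is who enters the trial: a site working from Section 8.1 turns away patients whom a site working from Section 7.2.1 admits. The second is how such patients are recorded. SAP Section 4.10.1 names inclusion and exclusion criteria as a category of major deviation, and such deviations can lead to removal from the per-protocol population. Section 13 of the protocol also makes a major deviation the trigger for a decision on whether the patient continues. SAP Section 1 says the plan is based on protocol version 7.0, but the SAP does not say which FEV1 limit defines a deviation.

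**Working it through.** No arithmetic lies behind either threshold, so the check is a comparison of the current texts.

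| Place | Threshold (pre-bronchodilator FEV1, % predicted) | Status |
|---|---|---|
| Protocol Section 2, criterion 7 | at least 25 | current, v7.0 |
| Protocol Section 7.2.1, criterion 7 | at least 25 | current, v7.0 |
| Protocol Section 8.1, Visit 1 spirometry | at least 30 | current, v7.0 |
| Protocol Section 9.1.6, Visit 1 spirometry | none of its own; refers to Section 7.2.1 | current, v7.0 |

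1. **Same quantity?** Yes. Every stated limit is for pre-bronchodilator FEV1 as a percentage of the predicted value. Section 9.1.6 uses the same reference equations as Section 8.1, so the choice of equations does not explain the gap.
2. **Same occasion?** Yes. Section 8.1 describes Visit 1, and Section 9.1.6 says the Visit 1 measurement serves to verify criterion 7. Section 8.1 lets spirometry from the preceding 30 days stand in for a new test. That changes when the value is obtained, not the limit it is held to.
3. **Current against superseded text?** No. The conflict is between operative sections of version 7.0. The change summary only shows how it may have arisen.
4. **Is precedence stated?** No passage in the protocol or SAP reconciles the two figures or ranks the sections.
5. **Who falls between them?** Patients with 25% ≤ FEV1 < 30% predicted, a band of 30 − 25 = 5 percentage points. At 27%, for example, a patient meets criterion 7 (27 ≥ 25) and fails Section 8.1 (27 < 30).
6. **How many?** The documents give no distribution of screening FEV1, so the number cannot be derived. Timing gives a partial bound. Version 7.0 is dated 22 October 2019, and Section 12 requires ethics committee and authority opinion before a substantial amendment is used. SAP Section 3.9 reports 342 randomised subjects in the data as of 15 January 2020 and 377 at the close of recruitment, so 377 − 342 = 35 were not in that data cut. An unknown further number were randomised under version 7.0 before it. These figures count randomised subjects only, so they do not bound the number turned away at screening.

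**The case against.** The best case on the other side accepts the mismatch and disputes its consequences.

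- **The criteria list governs in practice.** Section 7.2.1 says who can be included, Section 9.1.6 points to it, and the Visit 2 check in Section 8.2 is again against the criteria. Section 8 is introduced as an outline of procedures. This makes one reading more natural, but the limit in Section 8.1 is unqualified and nothing written sets it aside. That sites actually diverged is an inference; the documents show only that they could.
- **Section 8.1 does not call a low FEV1 a screen failure.** True: it attaches that label only to repeated negative sputum samples. A patient who misses a stated requirement at screening is nonetheless not eligible under that section.
- **The primary analysis is untouched.** This stands. It uses the mITT population, meaning all randomised subjects with at least one full or partial dose, and has no eligibility exclusion. Randomisation is 1:1 in blocks within site and macrolide stratum, so sites that read the limit differently do not bias the treatment comparison.
- **Per-protocol exclusion is not automatic.** This also stands. SAP Section 4.3 reports eligibility deviations by listed criterion, and a patient at 27% meets criterion 7. Exclusion further requires a judgement, made before unblinding, that the deviation could affect efficacy results. The risk is inconsistent coding, and the per-protocol analysis is supportive only.
- **It is late.** SAP Addendum Section 2.2 reports the database locked and the study unblinded, so a correction cannot change who was enrolled. It can still settle how the population and its deviations are described.

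**Conclusion.** The concern holds. As written, version 7.0 sets two different mandatory FEV1 limits for the same screening measurement, and Section 8.1 turns away patients whom criterion 7 admits. This is a wrong decision threshold in one of the operative sections, not merely missing detail.

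The effect is confined to patients with FEV1 from 25% to below 30% predicted who were screened under version 7.0, in unknown number. It bears on consistency of screening, the description of the enrolled population and the coding of eligibility deviations. It does not threaten the validity of the primary treatment comparison. The conclusion rests only on the wording of the sections compared, and it takes no view on which limit is clinically right.

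**What to change.** The sponsor should reconcile Section 8.1 with criterion 7 in Sections 2 and 7.2.1 so that one threshold appears throughout. Having Section 8.1 refer to criterion 7 without repeating a figure would prevent the two from drifting apart again. SAP Section 4.10.1 or the Blind Data Review and Analysis Sets Report should state which text defines an FEV1 eligibility deviation for the per-protocol set.

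Because recruitment is closed and the database locked, the trial report should also say which limit sites applied under version 7.0. It should give the number of screened and randomised patients in the 25% to below 30% band and how they were coded.

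The text change costs one figure or a clarification letter. The count needs only screening spirometry, wherever it was recorded. No change to the sample size or the primary analysis follows.

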8.2. VISIT 2 - RANDOMISATION VISIT (DAY 0)

At Visit 2 (Randomisation), the following procedures will be performed:

- check if subject is still eligible according to inclusion and exclusion criteria and check of screen failure criteria for Visit 2;
- documentation of concomitant medications (including azithromycin/erythromycin/clarithromycin use) or treatments;
- record details of any AEs since the Screening Visit (Visit 1);
- training and completion of CCI [REDACTED] on electronic clinical outcome assessment (eCOA) device before other study procedures;
- dip-stick pregnancy test for women of child-bearing potential.
- collection of CCI [REDACTED];
- randomisation by Interactive Web Response System (IWRS) and treatment kits assignment;
- dispensing of, and subject training on, CCI [REDACTED] device including the use of the [REDACTED] disc;
- subject training on IMP preparation, inhaled bronchodilator use and subject's card dispensing;
- first IMP administration under clinical supervision (at least 10 minutes after inhalation of short-acting bronchodilator; if the patient prefers not to use a bronchodilator this should be documented and the lack of bronchial hyper-reactivity after IMP administration documented);
- spirometry, including assessment of FEV₁ and FVC pre-bronchodilator and 30 ± 10 minutes post-IMP dose (**Note:** in case of a >15% decrease - not due to poor technique - in FEV₁ from pre-bronchodilator baseline after first IMP intake, or clinically determined bronchospasm, the subject will be immediately withdrawn from the trial);
- dispensing of sufficient IMP kits and inhaled bronchodilator for the treatment period until Visit 3;
- instruction of subjects on actions to be taken in case of CCI [REDACTED].

The Investigator will arrange an appointment for Visit 3 (28 days ± 1 week).

In addition, the Investigator will call the subject after 1 week to ensure that there are no problems with the mixing of IMP, the use of the nebuliser device and will also ask about any AEs, including any CCI [REDACTED] due to CCI [REDACTED], and any medical device malfunctions and/or incidents (see [Section 16.3.2](#)).

8.3. VISIT 3 (DAY 28 ± 1 WEEK)

At Visit 3, the following procedures will be performed:

- documentation of concomitant medications (including azithromycin/erythromycin/clarithromycin use) or treatments;
- check for occurrence of CCI [REDACTED] not reported by the subject (Note: whether an unreported CCI [REDACTED] occurred will be assessed retrospectively by the Investigator by asking about the prescription of antibiotics by other physicians; if yes, the CCI [REDACTED] and its duration will be recorded in the electronic Case Report Forms [eCRF]);
- record details of any AEs since previous visit;
- record details of any medical device malfunction and/or incidents since previous visit ([Section 16.3.2](#));
- record of CCI [REDACTED] and days of CCI [REDACTED] due to CCI [REDACTED];
- completion of CCI [REDACTED] on the eCOA device before other study procedures;
- dip-stick pregnancy test for women of child-bearing potential;
- blood samples for renal function tests ([Section 9.1.4](#));
- collection of CCI [REDACTED];
- spirometry, including assessment of FEV₁ and FVC;
- review of CCI [REDACTED] data using the data analyser provided to sites for the ongoing assessment of adherence (and re-training of subjects, if appropriate);
- IMP collection and accountability (used/unused vials), including check of bronchodilator use and dispensing of sufficient IMP kits and inhaled bronchodilator for the treatment period until Visit 4;
- instruction of subjects on actions to be taken in case of NCFB pulmonary exacerbations.

The Investigator will arrange an appointment for Visit 4 (within 2 months \pm 1week).

8.4. VISIT 4 (3 MONTHS \pm 1 WEEK) TO VISIT 6 (9 MONTHS \pm 1 WEEK), INCLUSIVE

At Visit 4 to Visit 6, inclusive, the following procedures will be performed:

- documentation of concomitant medications (including azithromycin/erythromycin/clarithromycin use) or treatments;
- check for occurrence of CCI [REDACTED] not reported by the subject (Note: whether an unreported CCI [REDACTED] occurred will be assessed retrospectively by the Investigator by asking about the prescription of antibiotics by other physicians; if yes, the CCI [REDACTED] and its duration will be recorded in the eCRF);
- record details of any AEs since previous visit;
- record details of any medical device malfunctions and/or incidents since previous visit ([Section 16.3.2](#));
- record of CCI [REDACTED] and days of CCI [REDACTED] due to CCI [REDACTED] since the previous visit;
- blood samples for clinical laboratory assessments (haematology, clinical chemistry and renal function tests) at Visit 5 only ([Section 9.1.4](#));
- completion of CCI [REDACTED] on eCOA device before study procedures;
- dip-stick pregnancy test for women of child-bearing potential;

- collection of CCI [REDACTED];
- spirometry, including assessment of FEV₁ and FVC;
- review of CCI data using the data analyser provided to sites for the ongoing assessment of adherence (and re-training of subjects, if appropriate);
- IMP collection and accountability (used/unused vials), including check of bronchodilator use and dispensing of sufficient IMP kits and inhaled bronchodilator for the treatment period until the subsequent visit;
- instruction of subjects on actions to be taken in case of NCFB pulmonary exacerbations.

The Investigator will arrange an appointment for the subsequent visit.

8.5. VISIT 7 (12 MONTHS ± 1 WEEK); END OF TREATMENT

At Visit 7, the following procedures will be performed:

- documentation of concomitant medications (including azithromycin/erythromycin/clarithromycin use) or treatments;
- check of occurrence of CCI [REDACTED] not reported by the subject (Note: whether an unreported CCI [REDACTED] occurred will be assessed retrospectively by the Investigator by asking about the prescription of antibiotics by other physicians; if yes, the CCI [REDACTED] and its duration will be recorded in the eCRF);
- record details of any AEs since previous visit;
- record details of any medical device malfunctions and/or incidents since previous visit ([See section 16.3.2](#));
- record of CCI [REDACTED] and days of CCI [REDACTED] due to CCI [REDACTED] since previous visit;
- completion of CCI [REDACTED] on eCOA device before any study procedures;
- assessment of vital signs ([Section 9.1.3](#));
- physical examination (including chest auscultation);
- 12-lead ECG in the supine position after 5 minutes of rest (with evaluation by local medical staff, [Section 9.1.6](#));
- dip-stick pregnancy test for women of child-bearing potential;
- blood samples for clinical laboratory assessments (haematology, clinical chemistry and renal function tests, [Section 9.1.4](#));
- collection of CCI [REDACTED];
- last IMP administration under clinical supervision (at least 10 minutes after inhalation of short-acting bronchodilator);
- spirometry, including assessment of FEV₁ and FVC pre-bronchodilator and 30 ± 10 minutes post-IMP dose;
- collection of CCI device and disc (to be transferred to CCI [REDACTED] for download);
- IMP collection and accountability (used/unused vials) and collection of bronchodilator.

8.6. FOLLOW-UP PHONE CALL (2 WEEKS ± 3 DAYS AFTER END OF TREATMENT)

A follow-up phone call will be performed at 2 weeks ± 3 days after the discontinuation of IMP.

The following procedures will be performed during the call:

- documentation of concomitant medications;
- AE monitoring.

If the result of the susceptibility test at the end of treatment (Visit 7) suggests the subject is resistant to colistin, he/she will be called for an extra visit with sputum collection for analysis of CCI [REDACTED].

8.7. EXACERBATION VISIT/CONTACT

Subjects will be trained by the Investigator to recognise signs and symptoms of NCFB pulmonary exacerbations.

At each post-randomisation visit the patient will be reminded about how to recognise symptoms of a NCFB pulmonary exacerbation and instructed to contact the site as soon as they have experienced these symptoms for 24 hours. If feasible, the subject will be asked to attend the clinic at their earliest convenience. If it is not practical for the subject to make an additional clinic visit then relevant information will be collected via phone and the subject will be asked to send a sputum sample to the clinic.

Any episodes of pneumonia during the trial should be considered as severe pulmonary exacerbations and will also require a clinic visit, if feasible.

The Investigator will decide if symptoms represent a NCFB pulmonary exacerbation meeting the protocol-defined criteria or not and on the appropriate course of action.

It will be clinically determined if the subject requires systemic antibiotic therapy (oral or intravenous) in addition to IMP administration or whether IMP administration should be temporarily interrupted (see below). Treatment of a NCFB pulmonary exacerbation will follow current treatment regimens used in the respective participating trial site.

If subjects need to be admitted to hospital for intravenous antibiotics, they should be visited by the research staff for an assessment within 72 hours of admission (where possible). If the subject is admitted to a hospital that is not the investigational site, the assessments should be carried out (where possible) by the admitting hospital under the direction of the investigational site. These assessments will include those collected during exacerbation visits/contacts and will include details regarding any interruption of IMP administration. In these circumstances, every effort should be made to complete all assessments although it is recognised that this might not be possible.

Telephone calls will be made to patients on a weekly basis during a NCFB pulmonary exacerbation until resolution to assess the progression of symptoms to and to determine whether systemic antibiotic treatment is ongoing. A telephone script will be provided to sites and responses to standardised questions will be collected in relevant eCRFs.

Resolution of a NCFB pulmonary exacerbation is defined as the date of completion of the required course of systemic antibiotic treatment or the Investigator's judgement that the NCFB pulmonary exacerbation has resolved, whichever is later. Exacerbations occurring less than 14 days after the end of a course of systemic antibiotics for a NCFB pulmonary exacerbation will be considered as a single event (see [Section 9.1.5](#)).

IMP administration may be temporarily interrupted during the time of systemic antibiotic treatment due to a pulmonary exacerbation based on the Investigator's judgement; thereafter, the study treatment should restart as soon as possible. Stop date and re-start

date will be recorded in the relevant eCRF. The occurrence of a pulmonary exacerbation does not mandate the discontinuation of the subject from the trial, unless it occurs between Visit 1 and Visit 2 and /or the Investigator believes discontinuation is in the subject's best interest.

The following assessment will be performed at an Exacerbation Visit or Phone contact, and all details of the pulmonary exacerbation have to be recorded:

- start date and duration of all symptoms since the start;
- all symptoms present which support the NCFB pulmonary exacerbation diagnosis;
- all concomitant medications, especially systemic antibiotics;
- physical examinations and vital signs (if attending the clinic);
- date of CCI [REDACTED] and/or days of CCI [REDACTED] (if any);
- measurement and recording of FEV₁ and FVC (if feasible);
- pulmonary exacerbation as AE/SAE according to protocol and followed until resolution, including weekly follow-up phone calls as detailed above;
- collection of CCI [REDACTED] for other antibacterial panels. If subjects are unable to attend the clinic then suitable arrangements will be made to obtain an additional CCI [REDACTED], if feasible.

